3.1.1 Sequence of treatment arms and cohorts

A dose level of BI 1387446 will always be explored as single agent first. Only once determined to be safe as single agent, this dose of BI 1387446 will be used in combination with ezabenlimab (BI 754091), always lagging at least one dose level behind when administered in combination with BI 754091.

[figure not shown]

Figure 3.1.1: 1 Sequence of cohorts. BI446: BI 1387446, PD1: ezabenlimab (BI 754091).

Patients with progressive disease on BI 1387446 monotherapy (Arm A) may cross over to the combination (Arm B) after completion of cycle 1 and will be treated at the highest dose level declared to be safe by the SMC at this time. These patients will continue treatment in combination by re-starting treatment at Cycle 1 Day 1 in Arm B. These patients will be analysed in Arm A as long as treated with monotherapy. Instead of completing the REP after monotherapy, patients may cross over to Arm B without repetition of all screening procedures, but will have to undergo a limited set of assessments as specified in [Section 6.2.1](#). A minimum interval of 7 days must have elapsed between last dose of BI 1387446 in Arm A and first dose of ezabenlimab (BI 754091) or BI 1387446 in Arm B. Cross-over patients will be included together with other 'backfill patients' (patients enrolled to backfill cohorts at dose levels that do not exceed the MTD, see [Section 3.1.2](#) for details) in the safety and efficacy assessment in Arm B, but will not be considered for the main analysis of the MTD. For the main analysis of the MTD, cross-over patients will only be included while being treated with BI 1387446 monotherapy in Arm A. However, cross-over patients will be included in the sensitivity analyses of the MTD and thus be considered in addition (refer to [Section 7](#) for details).

Arm B will open at the starting dose level once the starting dose level in Arm A is considered safe by the SMC.

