3. DESCRIPTION OF DESIGN AND TRIAL POPULATION

3.1 OVERALL TRIAL DESIGN AND PLAN

This study will consist of 3 arms, which will recruit patients in parallel with a clear predefined hierarchy for slot allocation ([Section 3.1.2](#)).

- Arm A: Dose escalation of BI 1387446 as single agent administered intratumourally into superficial lesions
- Arm B: Dose escalation of BI 1387446 administered intratumourally into superficial lesions, in combination with ezabenlimab (BI 754091) intravenously

Trial overview is shown in below Figure 3.1: 1.

[figure not shown]

Figure 3.1: 1 Trial overview

This study will determine the MTD as well as the safety, PK, and pharmacodynamics of BI 1387446 as monotherapy and in combination with ezabenlimab (BI 754091).

Arm A will determine the MTD for BI 1387446 intratumourally into superficial lesions as single agent. Patients with progressive disease may cross over to Arm B after completion of cycle 1, provided that Arm B is open for recruitment.

Arm B will determine the MTD for BI 1387446 intratumourally into superficial lesions in combination with ezabenlimab (BI 754091).

Arms A and B will investigate the safety, PK, and pharmacodynamics of BI 1387446 monotherapy (Arm A) or BI 1387446 in combination with ezabenlimab (BI 754091) (Arm B).

Arms A and B will start in a staggered manner (refer to [Section 3.1.1](#)).

To acquire additional data to more fully inform dose selection, additional patients may be enrolled to backfill cohorts at dose levels that have been previously cleared (refer to [Section 3.1.1](#)).

Dose escalation will be guided by Bayesian logistic regression modelling with overdose control: In Arm A and B, dose escalation will be guided by a BLRM using a hierarchical modelling approach to jointly model both arms. The data obtained from both arms will determine the MTD estimate per arm based on a BLRM employing an escalation with overdose control (EWOC) principle [[R13-4803](#)].

The BLRM estimates the MTD by updating estimates of the probability of observing a DLT in the MTD evaluation period (first treatment cycle including echocardiographic/MUGA scan measurements acquired on Day 1 of Cycle 2 and related findings) for each dose level in the trial as patient information becomes available. At any time in the trial, it will not be permitted to escalate to a dose which does not fulfil the EWOC criterion (refer to [Section 7](#)).

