3.1.2 Method of assigning patients to individual treatment cohorts

Treatment Arms A and B will be started sequentially. Arm A will start first. Once the first dose level in Arm A has been determined to be safe, Arm B may be initiated.

Minimum number of patients for each dose level within a treatment arm

Dose escalation decisions will be based on occurrence of DLTs.

Following the occurrence of a drug related Grade 2 or greater AE, excluding asymptomatic Grade 2 laboratory abnormalities that resolve without medical intervention within 48 hours and transient Grade 2 local injection site reactions that resolve within 48 hours (whereby supportive treatment is allowed), a minimum of 3 patients will be required per dose cohort. The SMC will decide on further trial conduct based on data from the minimum number of patients or can recommend to enroll additional patients at a given dose level.

Maximum number of patients for each dose level within a treatment arm

Once a dose cohort in a treatment arm has been determined to be safe and patient allocation to the next higher dose level is completed, additional patients may be enrolled into the same treatment arm at lower dose levels previously determined to be safe. This so called 'backfill' is intended to enlarge the safety and activity dataset, and to serve as a basis for selection of the RD-P2 in case of a non-linear dose-response relationship. A dose level in a treatment arm will not recruit more than 8 patients which have completed at least one treatment cycle, unless the SMC decides that more patients are needed to perform an adequate safety assessment or to account for patients who have crossed over from Arm A to Arm B. That is, each dose level in a treatment arm will enroll in the lower doses at least 1 patient, unless a Grade 2 or greater AE occurred (with the above exceptions), then at least 3 patients will be enrolled, and an intended maximum of 8 patients, and in the higher doses at least 3 patients and an intended maximum of 8 patients.

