4.1.4.3 Dose reductions and dose delays

As a general rule, any SAEs/AEs of \geq Grade 3 will result in a pause of treatment with BI 1387446 and/or ezabenlimab (BI 754091) until resolution to baseline or Grade 1.

In combination treatment arms, both drugs (BI 1387446 and ezabenlimab (BI 754091)) will be stopped, paused, or re-exposed together unless an AE can be attributed to either BI 1387446 or ezabenlimab (BI 754091). Only if a causal relationship to one trial drug can be unequivocally established, the other trial drug may be continued.

BI 1387446

Up to 2 dose reductions of BI 1387446 are allowed if the treatment pause due to an AE is \leq 12 weeks and the re exposure is considered clinically indicated by the Investigator.

Dose reductions will be only permitted to doses previously explored in lower dose levels. In case of re-occurrence or worsening of the same AE upon re-start of BI 1387446 at a lower dose, a second dose reduction of BI 1387446 is not permitted and BI 1387446 has to be permanently discontinued. Re-escalation to higher doses is not permitted. In case a third dose reduction would be required, treatment of that patient should be permanently discontinued. Treatment interruptions $>$ 12 weeks are only permitted for AEs not considered drug related and may be agreed on a case by case basis with the Sponsor.

Ezabenlimab (BI 754091)

Dose reductions or escalations of ezabenlimab (BI 754091) are not permitted. In case of adverse events, administration of ezabenlimab (BI 754091) should be delayed for up to 12 weeks to permit recovery from adverse events. Treatment interruptions $>$ 12 weeks are only permitted for AEs not considered drug related and may be agreed on a case by case basis with the Sponsor.

Infusion-related reactions

In the event of an infusion-related reaction \leq Grade 2, the infusion rate of ezabenlimab (BI 754091) may be decreased by 50% or interrupted until resolution of the event and re-initiated at 50% of the initial rate until completion of the infusion. In patients experiencing infusion-related reactions \leq Grade 2, subsequent infusions may be administered at 50% of the initial rate. If an infusion-related reaction is Grade 3 or higher in severity at any point during the study, treatment with ezabenlimab (BI 754091) has to be permanently discontinued.

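### The cross-over dosing rule in Protocol 3.1.1 has no cap for a patient dose-reduced in Arm A, so it conflicts with the re-escalation ban in 4.1.4.3 when the combination has been cleared above that patient's reduced dose

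*Protocol*

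**What the plan says.** **Cross-over dose.** Protocol 3.1.1 lets a patient who progresses on monotherapy move to the combination after cycle 1, restarting at Cycle 1 Day 1. Such a patient "will be treated at the highest dose level declared to be safe by the SMC at this time". SAP 6.1 repeats the rule. Protocol 3.1 adds one condition, "provided that Arm B is open for recruitment". Section 6.2.1 lists the assessments needed at cross-over: imaging, biopsies and echocardiography.

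**Dose reduction.** Protocol 4.1.4.3 allows up to two reductions of BI 1387446, to doses already explored at lower levels, and then states "Re-escalation to higher doses is not permitted". If the same event recurs or worsens at the lower dose, "a second dose reduction of BI 1387446 is not permitted and BI 1387446 has to be permanently discontinued". The overall limit is set per patient: "In case a third dose reduction would be required, treatment of that patient should be permanently discontinued".

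**Restart rules for particular toxicities.** Section 5.2.5 (LVEF decline) and Appendix 10.1.2 (Grade 3 immune-related events) both call for BI 1387446 to be resumed at a reduced dose.

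**Arm B's position.** A dose is explored as monotherapy first, with the combination "always lagging at least one dose level behind when administered in combination with BI 754091" (Section 3.1.1).

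**The concern.** Sections 3.1.1 and 4.1.4.3 are both worded as binding, and neither refers to the other. If a patient was reduced for toxicity in Arm A and Arm B has since cleared a higher level, a site that crosses the patient over must break one of them. If it follows 3.1.1, BI 1387446 goes up in someone who has already failed to tolerate a higher dose, at the moment a second immunotherapy is added. The protocol itself expects that combination may raise the rate and severity of immune-related events (Sections 1.2.3 and 1.4.2). What is at stake is the safety of individual patients and a clear instruction to sites.

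**Working it through.** The plan has no figure of its own on this point. The check sets the rules side by side and then asks whether the clash can occur under the plan's own escalation rules.

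**1. Is there a reconciling rule?** The conditions on cross-over are progression, completion of cycle 1, Arm B open, at least 7 days since the last Arm A dose, and the Section 6.2.1 assessments. None excludes a dose-reduced patient or caps the dose. Sections 4.1.4.3 and 3.3.4.1, which govern reductions and discontinuation, contain no exception for cross-over or change of arm.

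**2. When do the rules clash?** Number the dose levels in order and let:
- s = the patient's starting level in Arm A;
- m = the number of levels by which the dose was lowered, so the reduced level is r = s − m;
- a = the level Arm A has reached;
- b = the highest level cleared in Arm B, with b ≤ a − 1 from the lag rule.

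The rules clash when b > r, that is b ≥ s − m + 1. With b ≤ a − 1 this needs a ≥ s − m + 2.

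- m = 1: a ≥ s + 1 and b ≥ s. Arm A must have moved at least one level beyond the patient's starting level. The patient then returns to the level they were reduced from, or goes above it.
- m = 2: a ≥ s and b ≥ s − 1. No further escalation of Arm A is needed. At b = s − 1 the patient goes to an intermediate level, which breaches only the re-escalation ban.

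Section 4.1.4.3 does not limit a reduction to one level, so m = 2 can come from a single reduction.

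**3. Is this reachable?** Yes, by ordinary conduct. Arm A can escalate while the patient stays on treatment. Lower levels may need few patients to clear: "each dose level in a treatment arm will enroll in the lower doses at least 1 patient", subject to the Grade 2 rule in Section 3.1.2. Backfill patients begin below the current level by design: "additional patients may be enrolled into the same treatment arm at lower dose levels previously determined to be safe".

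**4. How large is the increase?** Section 4.1.2.1.1 limits each step between levels to 100%, so the ratio of assigned to reduced dose is at most 2^(b − r). With s = 3, m = 1 and r = 2:
- b = 3 gives at most 2^1 = 2;
- b = 4 gives at most 2^2 = 4.

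The actual dose levels are redacted, so these are upper bounds.

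**5. Do other safeguards close the gap?** The cross-over echocardiogram checks current LVEF. Section 5.2.5 requires a lower dose even after LVEF has recovered, so a normal scan does not restore the old dose. If the assigned level is at or above the one at which an LVEF decline or Grade 3 immune-related event occurred, those restart rules are defeated as well. SMC clearance is a judgement about a cohort, not about one patient's tolerance.

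**6. Does it reach the MTD?** Not in the main analysis. Protocol 3.1.1 and SAP 6.1 and 6.4 confine cross-over patients to their Arm A data there. Their Arm B data enter the Arm B safety and efficacy summaries, the sensitivity analyses in Protocol 7.2.2, and the supplementary model in SAP 7.4.4 if it is run.

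**7. With a cap.** Assigning the lower of b and r gives a level no higher than r in every case, so 4.1.4.3 is always met.

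**The case against.** The strongest reply is that cross-over restarts at Cycle 1 Day 1 and so opens a new course, in which nothing is being re-escalated. The text does not say this. Section 3.1.1 describes these patients as continuing treatment by restarting, and Sections 4.1.4.3 and 3.3.4.1 set their limits per patient and not per arm. That same per-patient wording suggests that Arm A reductions already count towards the limit of two, so stating it is a clarification. Likewise, the context of 3.1.1 points to Arm B as the arm in which the level must be safe; naming it removes any doubt.

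Second, cross-over is optional, so no site is forced into a breach. That is true, but the only escape it offers is to refuse cross-over, and no rule tells a site to do so.

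Third, the case needs several things together: a reduction for toxicity, later progression, a choice to cross over, and Arm B cleared above the reduced dose. Some toxicities already end treatment, including CRS of Grade 3 or higher for the drug held responsible, any use of an IL-6 antagonist, and several immune-related events. This stands, and it limits the weight of the point.

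A reader might also use the cohort intervals to date the clash to a particular tumour assessment, for example to rule it out at the Cycle 2 scan. The documents do not support that. A reduction can follow a pause of up to 12 weeks (Section 4.1.4.3), and Section 6.1 recalculates all later visits after a delay.

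**Conclusion.** The conflict is real and should be corrected. As written, 3.1.1 can assign a dose that 4.1.4.3 forbids, up to 2-fold the reduced dose for one level and up to 4-fold for two. It occurs exactly when the level cleared for the combination is above the patient's reduced dose.

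It is a safety point for a small subgroup. Few of the approximately 34 planned Arm A patients are likely to be concerned, but that is a judgement: the documents give neither a reduction rate nor a cross-over rate. A reader might infer that the MTD estimate is compromised. It is not, because the main analysis excludes cross-over patients' Arm B data. Nor can one say under which dose such a patient would be tabulated in Arm B: SAP 6.1 refers to the treatment first received after cross-over, while SAP 7.8 and 7.8.1 refer to the planned combination treatment.

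The conclusion assumes that the figures not shown and the SMC charter contain no overriding instruction. It matters only while Arm B is open to cross-over. SAP Section 4 says development has ended, Protocol 3.3.5 keeps consented patients on their treatment plan, and the documents do not say whether cross-over is still possible.

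**What to change.** Amend the cross-over sentence in Protocol 3.1.1 to read: *the highest dose level declared safe by the SMC in Arm B, but not above the patient's reduced dose if BI 1387446 was reduced in Arm A; reductions made in Arm A count towards the limit in 4.1.4.3.*

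The protocol sentence is the operative change, because the SAP does not direct dosing. Update the recital in SAP 6.1 for consistency only.

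The cost is one sentence in the protocol and a matching edit in the SAP. No patients, procedures or outputs are added; doses are already recorded in the eCRF (Protocol 4.3), and reductions are already reported (SAP 7.7 and 7.8.1).

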3.1.2 Method of assigning patients to individual treatment cohorts

Treatment Arms A and B will be started sequentially. Arm A will start first. Once the first dose level in Arm A has been determined to be safe, Arm B may be initiated.

Minimum number of patients for each dose level within a treatment arm

Dose escalation decisions will be based on occurrence of DLTs.

Following the occurrence of a drug related Grade 2 or greater AE, excluding asymptomatic Grade 2 laboratory abnormalities that resolve without medical intervention within 48 hours and transient Grade 2 local injection site reactions that resolve within 48 hours (whereby supportive treatment is allowed), a minimum of 3 patients will be required per dose cohort. The SMC will decide on further trial conduct based on data from the minimum number of patients or can recommend to enroll additional patients at a given dose level.

Maximum number of patients for each dose level within a treatment arm

Once a dose cohort in a treatment arm has been determined to be safe and patient allocation to the next higher dose level is completed, additional patients may be enrolled into the same treatment arm at lower dose levels previously determined to be safe. This so called 'backfill' is intended to enlarge the safety and activity dataset, and to serve as a basis for selection of the RD-P2 in case of a non-linear dose-response relationship. A dose level in a treatment arm will not recruit more than 8 patients which have completed at least one treatment cycle, unless the SMC decides that more patients are needed to perform an adequate safety assessment or to account for patients who have crossed over from Arm A to Arm B. That is, each dose level in a treatment arm will enroll in the lower doses at least 1 patient, unless a Grade 2 or greater AE occurred (with the above exceptions), then at least 3 patients will be enrolled, and an intended maximum of 8 patients, and in the higher doses at least 3 patients and an intended maximum of 8 patients.

Data from 'backfill' patients will be reviewed during the SMC meetings as well. That is, 'backfill' patients who have either experienced a DLT or have been observed for at least the MTD evaluation period without experiencing a DLT will be included into the main BLRM analysis at the next subsequent SMC meeting. Particularly, in case DLTs are observed in 'backfill' patients, this information may affect the magnitude of dose escalation or even result in dose de-escalation. Refer to [Section 7.2.2](#) for details.

Patient assignment rules

1. Treatment slots for dose escalation have priority over 'backfill' slots

Slots which are required for dose escalation decisions of the highest recruiting dose level will be allocated prior to 'backfill' slots.

2. Arm A has priority over Arm B

In case slots of the same priority (i.e. dose escalation or 'backfill') are open in arms A and B, and criteria 2 is met, patients will be recruited into Arm A prior to Arm B, unless Arm A is more than 2 dose levels ahead of Arm B.

Treatment start of individual patients within the same cohort

For all patients enrolled into a cohort required for DLT assessment, a minimum time period has to be elapsed between first treatment days of subsequent patients. In the first dose level in each arm, the second patient can receive the first dose of trial drug the earliest 7 days after the first patient has been dosed. For the second and all subsequent dose levels in a single treatment arm, a minimum of 3 days is required between the first dose to the first and second patient. For all subsequent patients prior to dose escalation in this arm, a 2 day interval is required. Only once a dose level has been determined safe by the SMC, subsequent patients ('backfill') may be dosed at the same day on this dose level in the respective treatment arm.

In case of the occurrence of DLTs, the SMC may decide about intervals between enrollment of patients, if applicable.

Table 3.1.2: 1

Minimum intervals between first dose of trial drug given to subsequent patients within the same cohort.

Dose	Patient 2	subsequent pts (prior to SMC/cohort safe)	subsequent pts ('backfill', post SMC/cohort safe)
Level 1	+7 days	+2 days	any time
Level ≥ 2	+3 days	+2 days	any time

3.1.3 Definition of superficial lesions

During screening, a projected lesion for injection needs to be selected.

Table 3.1.3: 1 Definition of superficial lesions

Definition	injected lesion outside of a body cavity
Location	skin subcutaneous intramuscular chest wall (without infiltration of visceral pleura) abdominal wall (without infiltration of intraabdominal structures)
Location	superficial lymph nodes (cervical, supra-/infraclavicular, axillary/pectoral, epitrochlear/brachial, inguinal, femoral, popliteal) superficial organs (salivary glands, thyroid, parathyroid, breast)
Dose escalation arm	A, B

3.2 DISCUSSION OF TRIAL DESIGN, INCLUDING THE CHOICE OF CONTROL GROUP(S)

Ezabenlimab (BI 754091) is expected to be required for efficacy due to the upregulation of PD-L1 following STING activation. This expectation is supported by internal and published preclinical data as well as clinical data on MK-1454 as monotherapy and in combination with pembrolizumab. Preclinical data for ADU-S100 indicate that the dose response relationship may be non-linear, possibly resulting in a decline in efficacy on non-injected lesions at higher doses. Thus, early combination with ezabenlimab (BI 754091) during dose finding is considered important for selection of a recommended dose for further development of BI 1387446.

In addition, a flexible enlargement of cohorts which have been confirmed to be safe by the SMC, the so called ‘backfill’ concept will be used to generate sufficient data at lower dose levels which appear relevant for dose selection and may only be identified during trial conduct.

BI 1387446 by its mode of action will increase cytokines, and thus has a potential risk to lead to cytokine release syndrome. Although there has been no increase of cytokines in preclinical

models for combination of BI 1387446 and ezabenlimab (BI 754091) compared to BI 1387446 alone, the trial design will ensure that a dose of BI 1387446 can only be tested in combination with ezabenlimab (BI 754091) if the same or a higher dose has been confirmed safe as monotherapy.

Dose escalation and cohort size will be determined based on the recommendation of the SMC, guided by a BLRM with overdose control. An escalation with overdose control design will increase the chance of treating patients at efficacious doses while reducing the risk of overdosing. This design is based on practical experience and is an efficient method due to its ability to identify the dose with a desired toxicity rate and its allocation of a greater proportion of patients to doses at, or close to, that desired dose [[R13-4802](#), [R13-4804](#), [R13-4805](#)]. The use of Bayesian models for Phase I studies has also been advocated by the EMA guideline on small populations [[R07-4856](#)] and by the FDA [[R13-4881](#)].

